7.3 TREATMENT REGIMENS

7.3.1 Steroid management (both arms)

Participants in each arm of the trial will continue to receive usual care for their relapsing PMR, including a long-term tapering course of steroid therapy, alongside any concomitant medications that may be clinically indicated to prevent or manage steroid side-effects.

If the PMR symptoms remain well-controlled during the steroid taper without any further relapses, and the participant is able to stop taking steroid entirely, they will be able to do so just as they do in usual care.

If there is a relapse of PMR disease activity, the steroid may be re-started, or the dose may be held constant for longer than originally planned, or the dose may be escalated; as in usual care this will be individualised to the participant according to the clinical discretion of the PI.

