7.4.2 Questionnaires

Throughout the trial, participants will be asked to complete questionnaires, which will be returned to either by post or electronically.

Every 4 weeks, participants will be sent a questionnaire relating to their current steroid dose, steroid dosing over each of the preceding 4 weeks, and whether the steroid dose had to be increased due to worsening of PMR symptoms.

In addition, every 12 weeks they will be asked to complete a more extensive questionnaire pack relating to their PMR and treatment-related symptoms, health-related quality of life and healthcare resource use. The questionnaires to be included in these packs are listed in section 14.10

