14.10 PARTICIPANT QUESTIONNAIRES

Participant-reported steroid dose, and whether this needed to be increased due to increase in PMR symptoms, will be collected via the Steroid Use Questionnaire. This questionnaire will be administered every four weeks from week 4 to week 80. Cumulative (prednisolone-equivalent) steroid dose will be estimated from data provided in the Steroid Use Questionnaire, interpolating if necessary. PMR relapse date(s) and date(s) of steroid cessation, if applicable, will be calculated from the data provided in the Steroid Use Questionnaire, allowing time to relapse, number of PMR relapses and time to steroid cessation and time to steroid-free remission to be calculated during the analysis of the trial.

PMR symptom severity will be captured via the PMR-IS administered at baseline (week 0) and weeks 12, 24, 36, 48, 60, 72 and 80 post randomisation.

Participant health related quality of life will be captured via the EQ-5D-5L questionnaire. This will be administered at baseline (week 0) and weeks 12, 24, 36, 48, 60, 72 and 80 post randomisation.

Participant healthcare resource use will be collected at baseline (week 0), and weeks 12, 24, 36, 48, 60, 72 and 80 post randomisation.

In addition, questionnaire booklets at baseline (week 0) and weeks 24 and 80 post baseline will include a Visual Analogue Scale (range 0 to 100mm) on which participants will mark the level of Pain they experience.

This will be used to score the PMR Activity Score. Booklets including this VAS will be distributed separately, as professional printing is required to ensure VAS lengths are exactly 100mm.

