16.2.2 Clinical outcomes

Time to steroid cessation

Time to steroid cessation, will be defined as the duration between date of randomisation and date at which participants report a current prednisolone dose of zero and there is sustained discontinuation of all steroids.

Sustained discontinuation of steroids will be defined as not taking any further steroids for the duration of follow-up.

Participants that have continued to take steroids/prednisolone to the end of follow-up or who had a temporary cessation of steroids will be censored at 18 months. Those who die, withdraw and/or are lost to follow-up will be censored at the point of death/withdrawal or loss to follow-up.

Time to steroid-free remission

Where participants report a current-oral steroid dose of zero a decision as to whether or not steroid-free remission is achieved will be agreed between the participant and physician at the week 80 assessment.

Time to PMR relapse

PMR relapse, which will be participant reported, will be defined as an increase in PMR symptoms sufficiently severe to require alteration of the steroid dosing plan. Participants will be asked every month whether they have had to adjust their planned steroid dosing plan due to an increase in PMR symptoms (participant reported relapse).

Time to PMR relapse will be defined as the duration between randomisation and date of PMR relapse. Participants that have not relapsed during follow-up will be censored at 18 months, or at date of death or withdrawal.

Note: There is no universally agreed definition of relapse in PMR, therefore, a pragmatic approach will be taken.

Number of PMR relapses

PMR relapse will be defined as an increase in PMR symptoms sufficiently severe to require alteration of the steroid dosing plan. The count of the number of PMR relapses will be derived as the sum of all relapses over the time at risk.

Time at risk will be defined as the duration between date of randomisation and the earliest of date of end of follow-up, death or withdrawal.

Cumulative (prednisolone-equivalent) steroid dose prescribed

Cumulative (prednisolone-equivalent) steroid dose prescribed over 18 months post randomisation.

The total amount of oral steroid prescribed during the trial will be assessed from GP records of all prednisolone prescriptions issued during the trial, and will be collected at 18 months post randomisation.

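### The relapse rules have no end-point for silent non-response, so months without a returned questionnaire count as relapse-free, and the protocol describes the monthly relapse question in two ways

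*Protocol*

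**What the plan says.** Section 16.2.2 of the protocol defines participant-reported relapse as "an increase in PMR symptoms sufficiently severe to require alteration of the steroid dosing plan". Its censoring rule for time to relapse is "Participants that have not relapsed during follow-up will be censored at 18 months, or at date of death or withdrawal". For the number of relapses, "Time at risk will be defined as the duration between date of randomisation and the earliest of date of end of follow-up, death or withdrawal"; section 18.3 uses that time as the offset in a negative binomial model.

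The rule for time to steroid cessation, also in 16.2.2, is fuller: "Those who die, withdraw and/or are lost to follow-up will be censored at the point of death/withdrawal or loss to follow-up".

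On the data source, section 14.10 says "PMR relapse date(s) and date(s) of steroid cessation, if applicable, will be calculated from the data provided in the Steroid Use Questionnaire". The form is sent every four weeks from week 4 to week 80 and asks about dosing in the preceding four weeks (7.4.2), so a later form does not cover a missed one.

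The protocol describes the relapse question in two ways. Section 16.2.2 says "Participants will be asked every month whether they have had to adjust their planned steroid dosing plan due to an increase in PMR symptoms". Section 7.4.2 says the form asks "whether the steroid dose had to be increased due to worsening of PMR symptoms", and 14.10 likewise refers to an increase. Section 7.3.1 lists among the possible responses to a relapse that "the dose may be held constant for longer than originally planned".

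**The concern.** Relapse can be seen only in months for which a form comes back, but neither relapse rule stops the clock when forms stop. Withdrawal is a documented event with its own form (13.4 Withdrawal of treatment, and 14.12), so a participant who simply stops replying has not withdrawn. Under the written rules that person stays at risk and relapse-free to 18 months. Skipped months likewise stay in the offset.

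Non-response is foreseen: 14.10 plans reminders, and section 17 allows 20% attrition. The trial is open label (7.1), so equal response in the two arms cannot be taken for granted. Time to relapse and number of relapses are named secondary objectives (6.3).

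The two descriptions of the question matter because a taper held for symptoms is an alteration of the dosing plan but not a dose increase. Whether it counts as a relapse depends on which description the questionnaire follows.

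**Working it through.** **The plan's own figures.** The protocol gives no power, event number or response rate for the relapse outcomes, so there is nothing to reproduce for them. The primary sample size does reproduce. The SD of log dose is √ln(1 + 0.78²) = 0.689 and the effect is |ln 0.70| = 0.357. Then 80 per arm gives 90.2% power, and 160 / 0.8 = 200. This point does not touch it.

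**Assumptions (not in the protocol).** Relapse is exponential with 50% relapsing by the end of follow-up. The true hazard and rate ratios are 1. A fraction *a* of an arm falls silent at a time uniform over follow-up, and none of these participants formally withdraws.

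**Observed relapse proportion when silent participants are carried to the end.**
- For someone silent from a uniform time, the mean chance that relapse was seen is 1 − 0.5/ln 2 = 0.279.
- Observed proportion = (1 − a) × 0.5 + a × 0.279 = 0.5 − 0.221a.
- At a = 0.20 this is 0.456, so about 46% is reported instead of 50%.

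**Hazard ratio**, approximated by the ratio of ln(1 − observed proportion):
- 15% usual care v 25% DMARD: observed 0.467 and 0.445; ln(0.555)/ln(0.533) = 0.588/0.629 = 0.94.
- Reverse: 0.629/0.588 = 1.07.

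**Rate ratio.** With a full-follow-up offset, an arm's observed rate is the true rate times (1 − a/2):
- 15% v 25%: 0.875/0.925 = 0.95. Reverse: 0.925/0.875 = 1.06.
- Equal loss of 20%: ratio 1.00, with both rates 10% too low (1 − 0.20/2 = 0.90).

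**Simulation check.** Cox models were fitted to 20,000 simulated participants per arm with four-weekly forms and a true hazard ratio of 1, for 50% and 70% relapse:

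| Silent loss, usual care v DMARD | HR, clock run to week 80 (50% / 70%) | HR, censored at last returned form (50% / 70%) | Rate ratio by formula |
|---|---|---|---|
| 20% v 20% | 1.00 / 0.99 | 1.00 / 0.99 | 1.00 |
| 15% v 25% | 0.93 / 0.94 | 1.00 / 1.00 | 0.95 |
| 25% v 15% | 1.06 / 1.08 | 1.00 / 1.01 | 1.06 |
| 10% v 30% | 0.90 / 0.87 | 1.02 / 1.00 | 0.89 |
| 30% v 10% | 1.14 / 1.16 | 1.01 / 1.02 | 1.12 |

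**Skipped months rather than drop-out.** If the arms differ in the share of forms returned, the rate ratio shifts by the ratio of those shares. Usual care 85% and DMARD 75% gives 0.75/0.85 = 0.88; the reverse gives 1.13.

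**If only half the loss is silent** (7.5% v 12.5%), the hazard ratio is ln(0.528)/ln(0.517) = 0.639/0.660 = 0.97.

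**The question wording, side by side.** The definition (16.2.2) is any alteration of the dosing plan for symptoms. The item in 16.2.2 is any adjustment, which matches. The item in 7.4.2 and 14.10 is an increase, which is narrower. A held dose (7.3.1) meets the definition and the first item but not the second. The protocol does not give the share of relapses handled that way, so no size can be put on this part.

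**The case against.** No sentence in the protocol says that unreturned months count as relapse-free. End of follow-up is not defined for a silent non-responder and could be read to include loss to follow-up. Section 18.5 allows imputation and promises sensitivity analyses, and 18.1 leaves detail to the SAP. That makes the relapse-free reading the literal default and not a certainty. It does not remove the problem. Both rules are spelled out, the neighbouring cessation rule names loss to follow-up where these do not, and 18.5 says only that outcomes may be imputed. A participant with an assigned censoring date would not be flagged as missing. Interpolation is named in 14.10 only for cumulative dose.

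Sites also review steroid use at weeks 4, 8, 12, 24, 36, 48, 60, 72 and 80 (14.6, 14.7), and some missing questionnaires are chased (19.4). This makes wholly silent loss rarer. However, 14.10 takes relapse dates from the questionnaire, and the site lists record steroid use, not relapse.

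The size is modest. With 200 participants and 50% relapsing there are about 100 events, so the standard error of the log hazard ratio is about 2/√100 = 0.20. A shift of ln 0.94 = −0.06 is about 0.3 of that.

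A reader might infer that the monthly question is simply too narrow and that held tapers go uncounted. The protocol does not support that: 16.2.2 describes a question that fits the definition, and the questionnaire itself is not shown. What stands is a contradiction between sections.

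**Conclusion.** The point holds as a fault in two secondary analyses. Followed literally, the relapse rules turn unobserved time into relapse-free time and make absolute relapse rates too low: about 46% instead of 50% at 20% silent loss.

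A reader might go further and infer that the hazard and rate ratios are biased, or biased in favour of DMARD. The protocol supports neither. Bias in the ratios needs silent non-response that differs by arm, no response rates are given, and the direction could be either. Under the stated assumptions a 10-point difference in silent loss moves a null hazard ratio to about 0.94 or 1.07 and a null rate ratio to about 0.95 or 1.06. Equal loss leaves both near 1.00, and the effect shrinks if only part of the loss is silent.

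The protocol also contradicts itself on what participants are asked each month. Under the wording in 7.4.2 and 14.10, relapses managed by holding the dose could be missed. The primary analysis and the sample size of 200 are unaffected.

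**What to change.** - **Time to relapse (16.2.2):** add loss to follow-up. Censor at the last period covered by a returned Steroid Use Questionnaire, or by a site steroid review if that review records relapse.
- **Number of relapses (16.2.2, 18.3):** define time at risk as the weeks so covered, so that skipped months leave the offset.
- **Sensitivity analysis:** these rules remove the bias only if non-response is unrelated to relapse. Pre-specify an analysis that relaxes this, and state how gaps before the last returned form are handled in the time-to-event analysis.
- **Question wording:** reconcile 7.4.2, 14.10 and 16.2.2 to one description that matches the relapse definition, and check the questionnaire against it.

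The cost is a few sentences in the protocol and SAP and at most one questionnaire item. The price in the analysis is slightly less follow-up time for these secondary outcomes.

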3. TRIAL SUMMARY

Trial Title	Steroid-Reducing Options for ReLapsING PMR (STERLING-PMR): a pragmatic, randomised trial to compare the clinical and cost-effectiveness of adding immunomodulation to steroid-tapering treatment for patients with relapsing PMR, versus steroid-tapering alone.
Short title	STERLING-PMR
Clinical Phase	Phase III
Study Sites	The Queen Elizabeth Hospital / University of Adelaide The Austin Hospital The University of Western Australia / Fiona Stanley Hospital
Trial Design	Multi-centre, Phase III, parallel-group, open-label, randomised controlled trial with internal pilot. The screening period of up to 6 weeks, a 80 week open label study period. At baseline, each subject will switch from oral glucocorticoids obtained from independent sources to oral prednisolone provided by the t the equivalent dose that the subject was taking just prior to the Baseline Visit, rounded up to the nearest 1 mg The study will consist of 4 study visits at site over 18 months. In addition, site research teams will conduct telephone assessments with participants from both arms at weeks 4, 8, 12, 36, 48, 60 and 72. Participants will be randomised in a 1:1 allocation ratio to receive either usual care alone or usual care plus DMARD.
Trial Participants	Patients with polymyalgia rheumatica (PMR) who are (1) receiving steroid treatment and (2) who have previously experienced at least one relapse of PMR.
Planned Sample Size	50 (of the 200 total)
Planned Number of Recruiting Sites	3
Follow-up schedule	7 study visits at site over 18 months (screening, baseline,12,24,36,48 and 80 weeks) In addition, site research teams will conduct telephone assessments with participants from both arms at weeks 4, 8, , 60 and 72. CTRU will manage the administration of monthly questionnaires sent to participant either by post or electronically.

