7.2 STUDY SETTING

The study will be conducted across a local hospital at each study site.. Each Participant site will search its own database of electronic medical records to identify potentially eligible participants who, if consenting and eligible, may be recruited by the site.

Once participants have been recruited to the trial, the site will have responsibility for the planned steroid taper along with the DMARD elements of the participant's care.

CALHN will obtain Ethics under the NHMRC national mutual acceptance scheme. All sites will act as research centres and hence will need to have obtained local Governance and management approvals and undertaken site initiation training with the CALHN trial coordinator prior to commencing recruitment into the trial.

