12.6 IMP Prescribing

Prescribing of DMARD and prednisolone taper be the responsibility of the site rheumatologist. Results of the most recent available blood monitoring tests must be checked before each new prescription of MTX and continuation of the taper schedule is issued and found to be acceptable relative to the parameters listed in section 13.4.1.

The prescriber should specify the day of intake on the prescription. Prescriptions will be sent to the local site pharmacy for dispensing. As the IMPs are generic hospital stocks being prescribed 'off-label' no trial-specific prescription is required. sites will use their local standard prescriptions. A note of the location of completed prescriptions should be stored in the Pharmacy Site File.

Where the site uses electronic prescribing programmes the pharmacy must provide verification that checks of the prescribing programmes have been made to ensure that the regimen is correct and authorised by the investigator or delegate.

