18.3 ANALYSIS OF SECONDARY OUTCOME MEASURES

PMR symptom severity measures, PMR activity score, and Patient-reported quality of life measures over 18 months: analysis of PMR-IS domain scores, health-related quality of life (EQ-5D-5L Utility), PMR-Activity Score will use multivariable repeated measures linear regression adjusting for minimisation factors, baseline value, treatment group, baseline-by-time interaction (if appropriate), age, time, and time-by-treatment group interaction. Centre will be fitted as a random effect, if feasible and has a positive variance component. Time will be fitted as a continuous variable, and the estimated time-by-treatment interaction effect with 95% CI and significance will be presented.

Time to steroid cessation, Time to PMR relapse: time to event will be calculated and summarised using Kaplan-Meier estimates. Adjusted hazard ratios will be estimated using Cox proportional hazards regression or parametric alternative, with covariates for minimisation factors (fitting centre as a random effect, if feasible) age and treatment group, and reported with 95% CI.

Steroid free remission at week 80 post randomisation will be summarised by treatment group and overall.

Number of relapses over time: A multivariable negative binomial regression model will be used to explore the number of relapses reported over follow-up time with an offset term for time at risk, adjusting for minimisation factors, age and treatment group. Centre random effects will be explored, assuming a Gamma distribution. Adjusted difference in rate of relapse with 95% CI will be reported.

Cumulative prednisolone-equivalent dose prescribed: A multivariable linear regression model will be fitted to log (cumulative glucocorticoid dose), adjusting for minimisation factors (fitting centre as a random effect, if feasible) age and treatment group. Adjusted mean fold difference in cumulative glucocorticoid dose with 95% CI will be reported.

Safety: The number of adverse events of special interest related to PMR or trial treatment, serious adverse events and SUSARs, in number of unique patients, will be reported by treatment received (MTX/LEF/Both/Neither) and by severity.

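### The secondary outcome of prescribed steroid dose is read from GP records only, although the protocol makes the site rheumatologist responsible for prescribing the prednisolone taper

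*Protocol*

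**What the plan says.** Section 16.2.2 (Clinical outcomes) lists cumulative prednisolone-equivalent steroid dose prescribed over 18 months as a secondary outcome. On its source it says: "The total amount of oral steroid prescribed during the trial will be assessed from GP records of all prednisolone prescriptions issued during the trial". The data are collected at 18 months, and steroids other than prednisolone are converted to an equivalent dose. Section 18.3 analyses the logarithm of this total by linear regression and reports an adjusted mean fold difference.

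Other sections place the prescribing elsewhere:

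- Section 12.6 (IMP Prescribing): "Prescribing of DMARD and prednisolone taper be the responsibility of the site rheumatologist".
- Section 7.2 (Study Setting), of the period after recruitment: "the site will have responsibility for the planned steroid taper along with the DMARD elements of the participant's care".
- Section 7.3.1, on re-starting, holding or escalating steroid at relapse: "as in usual care this will be individualised to the participant according to the clinical discretion of the PI".
- Section 3 (Trial Summary), on baseline: each subject is to "switch from oral glucocorticoids obtained from independent sources to oral prednisolone provided by the t the equivalent dose". The words naming the provider are not legible.

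Section 7.5 points the other way. GP practices that take part by sending out study information go on providing usual care for PMR.

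**The concern.** The outcome reads the records of a prescriber whom other sections have at least partly replaced. A prednisolone prescription written by the site rheumatologist would not be counted under the definition as it stands.

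The trial is open-label (Section 7.1). The primary outcome is reported by participants, and Section 16.1 acknowledges that little is known about the accuracy of participant-completed steroid diaries. The prescribed dose is the one steroid-dose outcome taken from prescribers' records, so it is the natural check on the primary result. If it misses part of the prescribing, disagreement between the two outcomes could reflect the data source rather than reporting error, and agreement would reassure less than it seems to.

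**Working it through.** **1. Does any section close the gap?**

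| Question | Where | Answer |
|---|---|---|
| Source of the outcome | 16.2.2 | GP records only |
| Who prescribes the taper | 12.6 | Site rheumatologist |
| Who is responsible for the taper after recruitment | 7.2 | Site |
| Who decides on steroid at relapse | 7.3.1 | PI |
| Are site steroid prescriptions copied to the GP record? | 13.1.9, 13.3.6 | Written dose notices to the GP appear in the methotrexate and leflunomide dosing sections; no steroid section has one |
| Is a prescription extract scheduled? | 14.2 | No row for GP or site prescriptions |
| Does the GP still prescribe steroid? | 7.5 | Possible; practices that send out study information continue usual care |

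So site-issued prednisolone is not counted, and the share this represents cannot be derived from the protocol.

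**2. The plan's own figure.** Section 17 gives 200 participants, 90% power, a 30% reduction, CV 0.78, two-sided 5% and 20% attrition. This is for the primary outcome.

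- Log-scale SD = √ln(1 + 0.78²) = 0.689; effect = −ln(0.70) = 0.357.
- The noncentral t calculation needs 80 evaluable per arm: 160 / 0.8 = 200. Power at 80 per arm is 90.2%.
- At CV 0.94 the log SD is 0.796 and power is 80.4%.

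The stated figures reproduce. The source of the prescribed-dose outcome does not enter them.

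**3. Effect on the level.** If GP records hold a share s of the prescribed steroid, the recorded dose is s times the true dose. Section 17 quotes a mean of 5 g over 18 months for relapsing PMR. With s = 0.5, an assumed value, the record would show 0.5 × 5 = 2.5 g.

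**4. Effect on the between-arm ratio.** For a common share within each arm,

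observed ratio = true ratio × (share in DMARD arm / share in usual care arm).

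The protocol gives no shares. For a true ratio of 0.70 and assumed shares from 0.5 to 1.0:

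| Share, usual care | Share, DMARD | Observed ratio |
|---|---|---|
| 1.0 | 1.0 | 0.70 |
| 0.5 | 0.5 | 0.70 |
| 1.0 | 0.75 | 0.525 |
| 0.75 | 1.0 | 0.933 |
| 1.0 | 0.5 | 0.35 |
| 0.5 | 1.0 | 1.40 |

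Equal capture leaves the ratio intact; only unequal capture moves it.

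**5. Zero totals.** For a participant whose prednisolone is all site-prescribed, the recorded total is 0 and ln(0) is undefined. The zero would come from the source, not from low steroid use.

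**The case against.** The strongest reply is that the GP remains in the picture. Section 7.5 keeps referring practices providing usual care for PMR, and Section 13 has both arms continuing usual care, so GP records may hold much of the steroid. This stands as far as the amount goes: the shortfall is undetermined, and large or universal zero totals are not shown. It does not remove the mismatch, since Section 7.5 is limited to practices that send out study information, while Sections 12.6 and 7.2 are not limited at all.

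Four stronger readings might be inferred and are not supported:

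- *The site supplies the prednisolone.* This rests on the garbled sentence in Section 3. Sections 12.2, 12.8 and 12.10 do not list prednisolone as an IMP, a dispensed item or a non-IMP. The point needs only the prescribing role.
- *The comparison is biased between arms.* Scheduled visits and calls are the same in both arms, and Sections 7.2 and 12.6 do not divide taper prescribing by arm.
- *Power falls.* If all 50 Australian participants (25% of 200) had zero totals and dropped out, 80 per arm would become 60 and power about 80%. But no power is stated for this secondary outcome, and the premise of universal zeros is not established.
- *Only prednisolone counts.* Section 16.2.2 converts other steroids. What remains open is route: it says oral, while Appendix 1 also covers intravenous, intramuscular and intra-articular steroid.

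It is also fair to say that a zero-handling rule belongs in the SAP. Such a rule could not recover prescriptions that the definition never collects. Site staff do review steroid use at calls and visits (Sections 14.6 and 14.7), but no prescription source is named for that review.

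**Conclusion.** The point holds for one secondary outcome and should be fixed before the 18-month data are collected. As written, the outcome omits site-issued prednisolone and understates the prescribed dose wherever the site prescribes. The size of the shortfall cannot be determined from the protocol. The ratio range of 0.35 to 1.40 around a true 0.70 depends on assumed GP shares of 0.5 to 1.0 and shows sensitivity, not an expected bias; under equal capture the ratio is unbiased. The conclusion rests on Sections 12.6 and 7.2 meaning what they say, and on no unstated arrangement that passes site steroid prescriptions into GP records. The primary outcome, its analysis and the sample size of 200 are untouched. What is lost is part of the value of a prescriber-recorded check on self-reported dose.

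**What to change.** 1. Reconcile Sections 3, 7.2, 7.5, 12.6 and 16.2.2 on who prescribes the steroid during the trial, and complete the broken sentence in Section 3.
2. Define the outcome in Section 16.2.2 as all steroid prescribed over the 18 months, taken from site prescription records and GP records combined and converted by Appendix 1.
3. Record the source of each entry and count each prescription once. Use dispensing records only to verify; adding them to prescriptions would count the same course twice.
4. State whether non-oral systemic steroid counts.

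With both sources in place a zero total becomes unlikely, since inclusion criterion 4 requires current steroid treatment. Any remaining rule for zeros can be left to the SAP.

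The cost is a wording change and one extra extract from site prescription records, with the work of matching it against the GP extract. Sample size and visits do not change.

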7.5 INTERACTION BETWEEN PRIMARY AND SECONDARY CARE

As in all instances where multiple medical teams are involved in care of a participant, accurate, concise and relevant interprofessional communication is required to ensure participants safety. Appropriate modes of communication, such as letter, telephone, email, fax, or electronic portals such as Advice and Guidance, will be utilised as necessary, depending on the degree of clinical urgency. This will be referred to as “in a timely fashion”.

GP practices who participate via sending their participants information about the study will continue to provide usual care for participants with PMR including ongoing management of relevant co-morbidities including diabetes, hypertension, osteoporosis and depression, including onward referral if necessary. If any clinical information salient to the management of such co-morbidities comes to the attention of the PI during the trial, the PI will inform the GP as appropriate.

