9.2.2 Participant Identification and Invitation – Secondary Care

Participants with PMR who are already under the care of a clinical team at the same site may also be invited to participate

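### Section 16.2.2 takes the secondary outcome of oral steroid prescribed from GP records alone, although 7.2 and 12.6 give the taper and its prescribing to the site

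*Protocol*

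**What the plan says.** Section 6.3 lists cumulative steroid dose prescribed among the secondary objectives. Section 16.2.2 defines it as all oral steroid prescribed over the trial period. It says the total "will be assessed from GP records of all prednisolone prescriptions issued during the trial", collected at 18 months, with other steroids converted to prednisolone equivalents. Section 18.3 analyses its logarithm by linear regression and reports an adjusted fold difference.

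On who prescribes, 7.2 states that once a participant is recruited, "the site will have responsibility for the planned steroid taper along with the DMARD elements" of care. Section 12.6 opens: "Prescribing of DMARD and prednisolone taper be the responsibility of the site rheumatologist". Section 7.3.1 leaves dose changes at relapse to the PI. The trial summary has participants move at baseline from steroid they had obtained independently to prednisolone provided to them; the name of the provider is garbled in the text.

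On the GP's role, 7.5 says that practices which send out study information "will continue to provide usual care for participants with PMR including ongoing management of relevant co-morbidities".

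**The concern.** The protocol gives a task to one party and counts it from another party's records. If sites prescribe the taper, the site holds the prescriptions that make up this outcome, and an extract from GP records alone omits them unless something carries them across.

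The outcome is worth getting right. The trial is open-label and its primary outcome is participant-reported. Section 16.1 itself notes how little is known about the accuracy of participant-completed steroid diaries. Prescribed dose is the records-based counterpart of the same quantity, so incomplete capture weakens the obvious comparison. Section 24.2.1 pools the Australian and UK data, so a shortfall would enter the main analysis of this outcome. An analysis plan could not repair it later, because the missing records would never have been collected.

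**Working it through.** The point is a conflict between sections. The plan attaches no figure to this outcome, so the texts come first and the arithmetic only illustrates scale.

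**1. Prescriber.** Sections 7.2 and 12.6 (first sentence) name the site. Section 7.3.1 and the trial summary point the same way. None of the four makes the GP the prescriber of the trial taper.

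**2. Source counted.** Section 16.2.2 names GP records and nothing else.

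**3. Other routes by which site prescriptions could be counted.**
- The steroid reviews at visits and telephone calls (14.2, 14.6, 14.7) and the Steroid Use Questionnaire (14.10) record what the participant takes, not what is prescribed.
- Sections 13.1.9 and 13.3.6 ask the GP to update the healthcare record when the MTX or LEF dose changes. There is no matching request for prednisolone.
- No section adds a site, hospital pharmacy or eCRF source of prednisolone prescriptions.

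So 16.2.2 counts site-issued prednisolone only where it happens to appear in the GP record.

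**4. Illustration of scale.** Inputs from section 17: mean cumulative dose 5 g over 18 months; Australian share 50/200 = 0.25. Assumption: a share s of prescribed prednisolone is site-issued and absent from the GP record. The protocol does not give s, so a range is shown. The last column also assumes complete UK capture and equal mean dose in the two countries.

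- Recorded dose = 5 × (1 − s)
- Share of the pooled total captured = 1 − 0.25 × s

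| s (assumed) | Recorded, true dose 5 g | Pooled share captured |
|---|---|---|
| 25% | 3.75 g | 93.75% |
| 50% | 2.5 g | 87.5% |
| 75% | 1.25 g | 81.25% |
| 100% | 0 g | 75% |

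**5. Effect on the comparison of arms.** On the log scale, recorded dose = log(true dose) + log(share captured). If the average log(share captured) is the same in both arms, it cancels: with half missed in each arm, a true ratio of 0.70 gives 0.70 × (0.5/0.5) = 0.70. Site is a minimisation factor (11.3) and 18.3 adjusts for those factors, so a shortfall uniform within a site is absorbed by the site term.

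**6. Primary outcome and power.** The sample size in section 17 concerns the participant-reported dose. It reproduces: 200 × (1 − 0.20) = 160, or 80 per arm; log SD = √ln(1 + 0.78²) = 0.689; difference = |ln 0.70| = 0.357; power by the t-test is 90.2%. This point changes none of it.

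**The case against.** The strongest reply is that the site may issue few of the prescriptions. Section 13 has both arms carrying on with usual care, and 7.5 keeps participating GP practices in that care. Being responsible for a taper does not mean writing every repeat prescription, and a GP record may list some hospital-issued prednisolone. This stands as a limit on size: the division between site and GP is unknown. It does not remove the conflict. Section 7.5 mainly describes co-morbidities and does not reverse 12.6, and if both parties prescribe, both sources are needed.

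A second reply concerns the rest of 12.6. The sentences "Prescriptions will be sent to the local site pharmacy for dispensing" and "A note of the location of completed prescriptions should be stored in the Pharmacy Site File" sit under a heading about IMPs, beside text on the day of intake. Prednisolone is neither an IMP nor a listed non-IMP (12.2, 12.10). A reader might infer that the site pharmacy dispenses prednisolone and files its prescriptions; the document does not support that. The point rests only on the opening sentence of 12.6, which names the prednisolone taper, and on 7.2.

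Two stronger readings are tempting:
- **Biased treatment effect.** This would need capture to differ by arm. Nothing in the protocol assigns steroid prescribing differently by arm, so any such figure would rest on invented shares.
- **Zero totals that break the log model.** The logarithm is undefined at zero, but this needs participants with no GP steroid prescription in 18 months. Section 9.2.2 allows recruitment of patients already under a site team but says nothing about who prescribes for them. Handling zeros is also commonly left to the analysis plan.

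**Conclusion.** The data source named in 16.2.2 does not match the prescribing arrangement in 7.2 and 12.6. Followed as written, the rule leaves out site-prescribed prednisolone that is not copied to the GP record, so the stated outcome can be under-counted.

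The reach is one secondary outcome in the 50 of 200 participants under this protocol; how UK sites prescribe cannot be read from this document. The amount lost is unknown, and the shares in the table are assumptions. No between-arm bias is shown, and the primary outcome and its power are unaffected. Confidence is high in the conflict of wording and low in how much data would be lost. It is a minor point, worth correcting before the 18-month records are collected.

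**What to change.** In 16.2.2, replace the sentence naming the source with:

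> assessed from site prescribing records and GP records of all oral steroid prescriptions issued between randomisation and 18 months, in both arms, each prescription counted once.

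This keeps the outcome to oral steroid, as 16.2.2 already defines it, and fits the existing rule that other steroids are converted.

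The cost is one further record extract per participant at the 18-month collection already planned, a check that a prescription found in both sources is not counted twice, and possibly a small eCRF change in the database shared with the UK. Section 12.9 requires no trial accountability log even for the IMPs, and prednisolone is not among them, so the extract would have to come from each site's ordinary prescribing records. Sites should confirm beforehand that these can be retrieved for both arms.
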